7.2. Screening and Critical Baseline Assessments

Cardiovascular medical history/risk factors (as detailed in the CRF) will be assessed at screening.

The following demographic parameters will be captured: year of birth, sex, race and ethnicity.

Medical/medication/family history will be assessed as related to the inclusion/exclusion criteria listed in Section 5.

7.3. Pharmacodynamics

7.3.1. FeNO measurements

Fractionated exhaled nitric oxide (FeNO) measurements will be collected from 7 days before Day 1 (start of treatment) (Day -7), and then every morning and evening all the way through to Day 35 of each treatment period (see Time and Events Table in Section 7.1). Additional time points may be added during the course of the study based on newly available information.

Single FeNO measurements will be collected at each time-point in accordance with ATS/ERS guidelines. These measurements will be recorded using a NIOX Vero device which will be supplied to the patient on Day -7 by the site. Measurements will be captured electronically and regularly downloaded by the site at each clinic visit.

Training and practice with these devices will be given to each patient at the screening visit.

More details will be given in the SRM.

7.3.2. Spirometry

Three technically acceptable FEV₁ measurements will be made at the time points outlined in the Time and Events table (Section 7.1) and the highest values will be recorded.

Spirometry assessments must be performed in accordance with ATS/ERS guidelines [ATS/ERS Task Force, 2005]. The Forced Expiratory Volume during the first 6 seconds (FVC₆), rather than the full Forced Vital Capacity (FVC) will be measured.

Screening FEV₁ must be measured between 7am-10am.

7.3.2.1. Reversibility testing

The presence of reversible airways disease can have been demonstrated historically within 6 months of the screening visit.

OR

It must be demonstrated at the screening visit.

Following the spirometry assessment at screening, administer a single dose of 400 µg inhaled albuterol / salbutamol using a metered dose inhaler (MDI) and spacer device. The bronchodilator will be withheld for 6 hours prior to the screening visit. At any time point between 15 and 30 minutes post administration of albuterol / salbutamol, take triplicate FEV₁ measurements and record the highest.

Reversibility is shown if there is an increase in FEV₁ of ≥ 12.0% over baseline **and** an absolute change of ≥ 200 mL between the highest pre and post salbutamol FEV₁.

7.3.2.2. FEV₁ Stability Limit

Calculate a FEV₁ Stability Limit as follows:

Best pre-dose FEV₁ x 80%

The FEV₁ Stability Limit value will be calculated at the pre-dose time point of treatment period 1 and used as reference until the pre-dose time point of treatment period 2. The stability limit will be re-calculated at the pre-dose time point of treatment period 2 and used for the remainder of the study.

7.3.3. PEF

Each subject will be given a PEF meter by the site on Day -7. Data will be captured electronically.

Subjects must measure morning and evening PEF as indicated in the time and events table. Three technically acceptable PEF measurements will be collected at each time point and the highest values will be recorded.

7.3.3.1. PEF Stability Limit

Subjects must have completed a minimum of at least 10 out of 14 peak flow measurements during the one week prior to randomisation (Day -7 to Day 1).

Calculate a PEF Stability Limit as follows:

Mean AM PEF from the available 7 days preceding Day 1 dose x 80%

The AM PEF from the morning of Day 1 will be included in the calculation of the PEF stability limit.

The PEF Stability Limit value will be used for the remainder of the study.

PEF devices will be set to alert the subject if their PEF drops below this limit.

7.3.3.2. PEF below Stability Limit

Should the PEF fall below the PEF stability limit, the subject should contact the site. The investigator must monitor the subject and withdraw the subject if he/she meets any of the criteria in Section [5.4](#).

7.4. Safety

Planned time points for all safety assessments are listed in the Time and Events Table (Section 7.1). Additional time points for safety tests (such as vital signs and physical examinations) may be added during the course of the study based on newly available data to ensure appropriate safety monitoring.

7.4.1. Adverse Events (AE) and Serious Adverse Events (SAEs)

The definitions of an AE or SAE can be found in [Appendix 2](#).

The investigator and their designees are responsible for detecting, documenting and reporting events that meet the definition of an AE or SAE.

7.4.1.1. Time period and Frequency for collecting AE and SAE information

- Any SAEs assessed as related to study participation (e.g., protocol-mandated procedures, invasive tests, or change in existing therapy) or related to a GSK product will be recorded from the time a subject consents to participate in the study up to and including any follow-up contact.
- AEs will be collected from the start of the run-in period (Day -7) until the follow-up contact (see Section 7.4.1.3), at the time-points specified in the Time and Events Table (Section 7.1).
- Medical occurrences that begin prior to the start of study treatment but after obtaining informed consent may be recorded on the Medical History/Current Medical Conditions section of the CRF.
- All SAEs will be recorded and reported to GSK within 24 hours, as indicated in [Appendix 2](#).
- Investigators are not obligated to actively seek AEs or SAEs in former study subjects. However, if the investigator learns of any SAE, including a death, at any time after a subject has been discharged from the study, and he/she considers the event reasonably related to the study treatment or study participation, the investigator must promptly notify GSK.

NOTE: The method of recording, evaluating and assessing causality of AEs and SAEs plus procedures for completing and transmitting SAE reports to GSK are provided in [Appendix 2](#).

7.4.1.2. Method of Detecting AEs and SAEs

Care will be taken not to introduce bias when detecting AEs and/or SAEs. Open-ended and non-leading verbal questioning of the subject is the preferred method to inquire about AE occurrence. Appropriate questions include:

- “How are you feeling?”
- “Have you had any (other) medical problems since your last visit/contact?”

- “Have you taken any new medicines, other than those provided in this study, since your last visit/contact?”

7.4.1.3. Follow-up of AEs and SAEs

After the initial AE/SAE report, the investigator is required to proactively follow each subject at subsequent visits/contacts. All SAEs, and non-serious AEs of special interest (as defined in Section 4.6.1) will be followed until resolution, until the condition stabilizes, until the event is otherwise explained, or until the subject is lost to follow-up (as defined in Section 5.4). Further information on follow-up procedures is given in [Appendix 2](#).

7.4.1.4. Cardiovascular and Death Events

Investigators will be required to fill out event specific data collection tools for the following AEs and SAEs:

- Myocardial infarction/unstable angina
- Congestive heart failure
- Arrhythmias
- Valvulopathy
- Pulmonary hypertension
- Cerebrovascular events/stroke and transient ischemic attack
- Peripheral arterial thrombosis
- Deep Venous Thrombosis
- Revascularization

For these cardiovascular events detailed above and for all deaths, whether or not they are considered SAEs, specific Cardiovascular (CV) and Death sections of the CRF will be required to be completed. These sections include questions regarding cardiovascular (including sudden cardiac death) and non-cardiovascular death.

The CV CRFs are presented as queries in response to reporting of certain CV Medical Dictionary for Regulatory Activities (MedDRA) terms. The CV information should be recorded in the specific cardiovascular section of the CRF within one week of receipt of a CV Event data query prompting its completion.

The Death CRF is provided immediately after the occurrence or outcome of death is reported. Initial and follow-up reports regarding death must be completed within one week of when the death is reported.

7.4.1.5. Disease-Related Events and/or Disease-Related Outcomes Not Qualifying as SAEs

The following disease related events (DREs) are common in subjects with asthma and can be serious/life threatening:

1. Wheezing
2. Chest tightness or chest heaviness
3. Coughing

Because these events are typically associated with the disease under study, they will not be reported according to the standard process for expedited reporting of SAEs to GSK (even though the event may meet the definition of a SAE). These events will be recorded on the DRE page in the subject's CRF within 5 working days.

NOTE: However, if either of the following conditions apply, then the event must be recorded and reported as an SAE (instead of a DRE):

- *The event is, in the investigator's opinion, of greater intensity, frequency, or duration than expected for the individual subject, or*
- *The investigator considers that there is a reasonable possibility that the event was related to treatment with the investigational product*

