4.6.1. Risk Assessment

| Potential Risk of Clinical Significance | Mitigation Strategy | Monitoring implemented |
|--|---|---|
| Investigational Product (IP) | | |
| There is a potential risk of worsening asthma as subjects will receive placebo in one treatment arm and no treatments during the washout periods (however access to SABA rescue medication will be available throughout the entire study). | Stopping criteria will be applied for both FEV ₁ (during the clinic stays/visits) and PEF (out-patient and in-clinic) which will be monitored throughout the study treatment and washout periods. | Stopping criteria will be applied for both FEV ₁ (during the clinic stays) and PEF (out-patient and in-clinic) which will be monitored throughout the study treatment and washout periods. |
| As with any inhaled medication paradoxical bronchospasm may occur with an immediate wheeze after dosing. | If bronchospasm occurs following dosing, immediate administration of a short-acting (i.e., quick relief) inhaled bronchodilator (e.g., albuterol) is recommended. If this treatment fails to provide relief, a physician should be contacted immediately and/or emergency treatment should be sought. | First dose of the study medication in each treatment period will be administered in the clinic under the supervision of a physician. |
| FF/VI is contraindicated in subjects with severe milk protein allergy or known hypersensitivity or any ingredient of the preparation. | These subjects will be excluded from the study. | Not applicable. |
| Cardiovascular effects, such as cardiac arrhythmias e.g. supraventricular tachycardia and extrasystoles may be seen with sympathomimetic drugs, including fluticasone furoate/vilanterol. Therefore fluticasone furoate/vilanterol should be used with caution in patients with severe cardiovascular disease. | Caution is needed in patients with pre-existing cardiovascular (CV) disease, especially severe CV disease. Patients with severe CV disease will be excluded. | Not applicable |

| Potential Risk of Clinical Significance | Mitigation Strategy | Monitoring implemented |
|---|--|---|
| Investigational Product (IP) | | |

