12.2.1. Definition of Adverse Events

Adverse Event Definition:

- An AE is any untoward medical occurrence in a patient or clinical investigation subject, temporally associated with the use of a medicinal product, whether or not considered related to the medicinal product.
- NOTE: An AE can therefore be any unfavorable and unintended sign (including an abnormal laboratory finding), symptom, or disease (new or exacerbated) temporally associated with the use of a medicinal product.

Events meeting AE definition include:

- Any abnormal laboratory test results (hematology, clinical chemistry, or urinalysis) or other safety assessments (e.g., ECGs, radiological scans, vital signs measurements), including those that worsen from baseline, and felt to be clinically significant in the medical and scientific judgement of the investigator.
- Exacerbation of a chronic or intermittent pre-existing condition including either an increase in frequency and/or intensity of the condition.
- New conditions detected or diagnosed after study treatment administration even though it may have been present prior to the start of the study.
- Signs, symptoms, or the clinical sequelae of a suspected interaction.
- Signs, symptoms, or the clinical sequelae of a suspected overdose of either study treatment or a concomitant medication (overdose per se will not be reported as an AE/SAE unless this is an intentional overdose taken with possible suicidal/self-harming intent. This should be reported regardless of sequelae).

Events NOT meeting definition of an AE include:

- Any clinically significant abnormal laboratory findings or other abnormal safety assessments which are associated with the underlying disease, unless judged by the investigator to be more severe than expected for the subject's condition.
- The disease/disorder being studied or expected progression, signs, or symptoms of the disease/disorder being studied, unless more severe than expected for the subject's condition.
- Medical or surgical procedure (e.g., endoscopy, appendectomy): the condition that leads to the procedure is an AE.
- Situations where an untoward medical occurrence did not occur (social and/or

convenience admission to a hospital).

- Anticipated day-to-day fluctuations of pre-existing disease(s) or condition(s) present or detected at the start of the study that do not worsen.

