12.2.2. Definition of Serious Adverse Events

If an event is not an AE per definition above, then it cannot be an SAE even if serious conditions are met (e.g., hospitalization for signs/symptoms of the disease under study, death due to progression of disease, etc).

Serious Adverse Event (SAE) is defined as any untoward medical occurrence that, at any dose:

a. Results in death

b. Is life-threatening

NOTE:

The term 'life-threatening' in the definition of 'serious' refers to an event in which the subject was at risk of death at the time of the event. It does not refer to an event, which hypothetically might have caused death, if it were more severe.

c. Requires hospitalization or prolongation of existing hospitalization

NOTE:

- In general, hospitalization signifies that the subject has been detained (usually involving at least an overnight stay) at the hospital or emergency ward for observation and/or treatment that would not have been appropriate in the physician's office or out-patient setting. Complications that occur during hospitalization are AEs. If a complication prolongs hospitalization or fulfills any other serious criteria, the event is serious. When in doubt as to whether "hospitalization" occurred or was necessary, the AE should be considered serious.
- Hospitalization for elective treatment of a pre-existing condition that did not worsen from baseline is not considered an AE.

d. Results in disability/incapacity

NOTE:

- The term disability means a substantial disruption of a person's ability to conduct normal life functions.
- This definition is not intended to include experiences of relatively minor medical significance such as uncomplicated headache, nausea, vomiting, diarrhea, influenza, and accidental trauma (e.g. sprained ankle) which may interfere or prevent everyday life functions but do not constitute a substantial disruption

| |
|---|
| 
e. Is a congenital anomaly/birth defect
 |

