9.2. Overview of Safety Analyses

9.2.1. Overview of Planned Adverse Events Analyses

The safety analyses will be based on the “All Subjects” population, unless otherwise specified.

[Table 6](#) provides an overview of the planned analyses, with further details of data displays being presented in [Appendix 10](#): List of Data Displays.

Table 6 Overview of Planned Adverse Event Analyses

Endpoint	Absolute		
	Summary		Individual
	T	F	L
Adverse Events (AEs)			
All AEs by SOC and PT	Y		Y
Drug-Related AEs by SOC and PT	Y		
Subject Numbers for Individual AEs			Y
Relationship Between AE SOC, PT and Verbatim Text			Y
Serious AEs by SOC and PT			Y
AEs Leading to Withdrawal from Study / Permanent Discontinuation of Study Treatment by SOC and PT	Y		Y

NOTES:

- T = Table, F = Figures, L = Listings, Y = Yes display generated, SOC = System Organ Class, PT = Preferred Term.
- Summary = Represents TF related to any summaries (i.e. descriptive statistics) of the observed raw data.
- Individual = Represents FL related to any displays of individual subject observed raw data.

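### The SAP plans no display of the disease-related-event page, so wheeze, chest tightness and cough left on it are collected but not reported, and worsening asthma is reported only partly and indirectly

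*Protocol*

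**What the plan says.** Protocol 4.6.1 opens its risk table with worsening asthma: "There is a potential risk of worsening asthma as subjects will receive placebo in one treatment arm and no treatments during the washout periods". The second row is "As with any inhaled medication paradoxical bronchospasm may occur with an immediate wheeze after dosing".

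Protocol 7.4.1.5, within the Safety section, names wheezing, chest tightness or heaviness, and coughing as disease-related events and accepts that they can be serious or life-threatening. On routing it says "they will not be reported according to the standard process for expedited reporting of SAEs to GSK" and "These events will be recorded on the DRE page". Two exceptions send an event to SAE reporting instead: it exceeds what is expected for that subject in intensity, frequency or duration, or a link to the product is reasonably possible.

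Protocol 12.2.1 lists among things that are not AEs "The disease/disorder being studied or expected progression, signs, or symptoms of the disease/disorder being studied, unless more severe than expected". The same section counts an exacerbation of a pre-existing condition as an AE. Protocol 12.2.2 adds that what is not an AE cannot be an SAE, and gives "hospitalization for signs/symptoms of the disease under study" as an example.

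Protocol 9.4.3 commits to listing and summarising safety data. SAP 2.1 reports no departure from the protocol's analysis. SAP 9.2 and Appendix 10 then set out the safety displays.

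**The concern.** A separate CRF page for expected disease symptoms is a reasonable way to keep them out of expedited reporting. It becomes a reporting problem when no output is planned for the page. The symptoms diverted here are those by which the first two risks in the protocol's own risk table would show themselves, and the page can hold events that met a seriousness criterion.

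The design makes this more than a formality. A subject who completes both periods nominally spends 14 days on placebo, 21 to 49 days off treatment after Period 1 (21 days of monitoring plus a gap of 0 to 28 days) and 21 days off treatment after Period 2. The trial asks how long the effect of FF/VI lasts once it stops, and the return of symptoms is the clinical counterpart of the return of FeNO. No planned output shows symptoms at the subject's expected level by treatment, or during dosing against after dosing.

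**Working it through.** No formula applies. The check is a count of the planned displays, followed by a comparison of the routing rules.

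**1. Displays.** SAP 11.10.1 numbers them:
- tables: 10 (study population) + 8 (pharmacodynamic) + 3 (safety) + 2 (biomarker) = 23
- figures: 6 + 1 = 7
- listings: 18 (ICH) + 7 (other) = 25
- total: 23 + 7 + 25 = 55

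Read title by title in SAP 11.10.4 to 11.10.11, 0 of 55 name the DRE page, and none is dedicated to exacerbations, to the asthma criteria in Protocol 5.4 or to rescue use. All 3 safety tables are AE tables. Listings 13 to 16 and 19 are AE or SAE listings; 17 and 18 are vital signs and laboratory data. SAP Table 6 has AE and SAE rows only.

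**2. Where an episode of wheeze, tightness or cough goes.**

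| Episode | Protocol 7.4.1.5 | Protocol 12.2.1 and 12.2.2 | SAP display |
|---|---|---|---|
| Expected level, not thought related, a seriousness criterion met | DRE page | Not an AE, so not an SAE | None |
| Expected level, not thought related, not serious | DRE page, or silent if the section covers only otherwise-serious events | Not an AE | None |
| More frequent than expected, not more severe | SAE | AE under the exacerbation bullet; not an AE under the exclusion, and then not an SAE | Depends on which rule is followed |
| Expected level, possibly related | SAE | Not an AE under the exclusion, so not an SAE | Depends on which rule is followed |
| More severe than expected | SAE | AE; SAE if a criterion is met | Table 3.1, Listings 13 and 14; Listing 15 if an SAE |
| Leads to withdrawal under Protocol 5.4 | Any of the above | Any of the above | Table 1.1 and Listing 2; also Table 3.3 and Listing 16 if an AE |

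The first two rows show the reporting gap: unless the subject also withdraws, nothing planned displays the event. The third and fourth rows show that the protocol sections conflict. The exception in 7.4.1.5 turns on intensity, frequency, duration or relatedness, whereas the exclusion in 12.2.1 turns on severity alone.

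**3. Against the commitments.** DREs are collected under the protocol's Safety section, Protocol 9.4.3 covers safety data without exception, and SAP 2.1 declares no change. The SAP therefore falls short of the protocol for this one category.

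**The case against.** The strongest reply is that worsening asthma does reach the safety outputs. A reader might infer that the first-named risk is missing from them, or that asthma worsening is largely excluded from the AE and SAE definitions. The documents support neither reading. Events worse than expected or possibly related must be reported as SAEs, and exacerbation of a pre-existing condition is an AE. Protocol 5.4 withdraws any randomised subject who meets an asthma criterion, which puts that subject in Table 1.1 and Listing 2. Where the event is an AE, it also falls under the SAP Table 6 row "AEs Leading to Withdrawal from Study / Permanent Discontinuation of Study Treatment by SOC and PT". FEV1 displays are planned too. This stands, and it limits the point to what stays on the DRE page.

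A second reply is that 7.4.1.5 concerns expedited reporting and may cover only events that would otherwise be serious. That is a plausible reading. It would make the page shorter, but what remained on it would be the otherwise-serious events, and those would still have no display.

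Third, SAP Appendix 4 already defines on-treatment and post-treatment states. It does so for AE dates, however, and is not applied to DREs.

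A reader might also infer that Table 3.2 under-counts drug-related wheeze. The documents do not show this: a possible link to treatment sends the event to SAE reporting, and nothing makes the DRE page the investigator's default. Nor is routing under the blind a flaw, since blinding limits differential classification. Finally, the low-risk statement in Protocol 4.6.3 is a pre-study judgement that this trial was not designed to verify.

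PEF is only a partial substitute. SAP Table 4 marks a PEF table and listing, but no title in Appendix 10 names PEF.

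**Conclusion.** The point holds in limited form. The DRE page has 0 of 55 planned displays, against a protocol commitment to list and summarise safety data. Events left on it, including any that met a seriousness criterion, would be collected and not reported. Worsening asthma is reported partly and indirectly, through AE, SAE and withdrawal displays; it is not absent.

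The size in events is unknown. The documents give no expected symptom rate and do not settle whether non-serious symptoms belong on the page. The conclusion assumes that the display list is followed as numbered and that no DRE data are merged into the AE dataset, which neither document mentions. The primary FeNO analysis is not affected. The SAP should be corrected before unblinding.

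**What to change.** In SAP 9.2.1 and Appendix 10, add:

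1. A listing of DREs.
2. A summary of DREs by treatment and treatment state (on-treatment; post-treatment, with the gap of up to 4 weeks before Period 2 included and assigned to the Period 1 treatment). The definitions in SAP Appendix 4 need extending to DRE dates.
3. A combined AE and DRE summary, so that counts do not depend on which page the investigator used.

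Reconcile Protocol 7.4.1.5, 12.2.1 and 12.2.2 on which asthma events go to which page. This review takes no view on which rule should prevail.

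Optionally, flag in Listing 2 which Protocol 5.4 criterion led to each withdrawal, where the CRF records it.

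The cost is SAP wording, a few programmed displays and a clarification of the protocol. The combined summary will show more events than the AE table alone, and the report should explain why. The CRF is not among the documents, so it should not be assumed that every useful field exists. In particular, they do not say whether DRE onset clock time or daily rescue inhalation counts are captured, so the displays above are framed without them.
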